## Title:

### Feasibility Trial of a Lifestyle Intervention for Pregnant People with Gestational Diabetes

#### Summary/Background:

Gestational diabetes mellitus, or GDM, affects 2-10% of pregnancies in the United States (CDC). Approximately 50% of patients with GDM will progress to develop Type 2 diabetes in their lifetime. Patients must have immediate access to nutrient-rich food and ongoing education and support regarding healthy meal preparation. GDM, therefore, is a perfect window of opportunity for prevention of diabetes. The opportunity provided by a diagnosis of GDM can be utilized only if optimal medical and obstetric care and sustainable educational interventions are provided to patients who are pregnant with GDM.

The socioeconomic impact of GDM is significant. Dietary non-compliance and poor reliability of glucose monitoring increase adverse pregnancy outcomes. Compared with pregnancies without GDM, women with GDM are more likely to have pregnancy complications, including antepartum hospitalization, cesarean delivery (50.3% vs 35.3%), and a longer length of stay during antepartum or delivery admissions. Infants of mothers with GDM are more likely to suffer several adverse neonatal outcomes, including metabolic and hematologic disorders, respiratory distress, cardiac disorders, and neurologic impairment due to perinatal asphyxia and birth traumas, and higher rates of admission to the neonatal intensive care unit.

Optimal outcomes in patients who are pregnant with GDM require education and adoption of an ADA-specific diet, daily glucose monitoring and physical activity, and compliance with prenatal visits. To improve pregnancy outcomes, patients must understand and adopt these interventions on a significantly accelerated pathway compared with patients who are not pregnant as, on average, patients with GDM will have 8 to 10 weeks before they deliver. Thus, to achieve these goals quickly, patients must have immediate access to nutrient-rich food and on-going education and support regarding healthy meal preparation, including portion sizes, frequency, and composition of healthy snacking. There are ongoing studies on subsidized healthy food prescription programs to assess meaningful changes in average blood glucose levels and other clinically relevant outcomes in type 2 diabetes, however similar trials have yet to be performed in patients with GDM.

Most previous exercise interventions for blood glucose control in patients who are pregnant with GDM have included supervised exercise sessions and thus are difficult to translate to the health care system. Lifestyle interventions that promote self-efficacy with unsupervised exercise and evidence-based behavioral strategies (e.g., goal setting, monitoring, and feedback) and incorporate the use of physical activity tracking devices to support these strategies are needed.

### Aims and Objectives:

This study will assess the feasibility of a community-based lifestyle intervention called Meals for Mom (M4M) for pregnant persons diagnosed with gestational diabetes (GDM). In previous work, we developed the intervention and received feedback from women living with gestational diabetes via focus groups (UCONN IRB # 23-190SSF-2).

The Specific Aim of this project is to conduct a pilot feasibility randomized clinical trial of Meals for Moms (M4M) program in patients diagnosed with gestational diabetes. Feasibility outcomes include recruitment, retention, intervention receipt, and program acceptability. We will also measure and describe clinical

outcomes (e.g., diet quality, average glucose values, need for insulin, Cesarean delivery and NICU admission) that will be primary outcomes of a subsequent efficacy trial.

### Study Design:

The study has been designed to take place in two distinct phases: Phase 1 – Development of the Meals 4 Moms Program and Phase 2: Feasibility Randomized Control Trial (see enclosed grant proposal). We used feedback from the focus groups conducted in Phase 1 to inform the development of the intervention. **This study protocol covers Phase 2 – the feasibility pilot trial.**

Study participants will be invited to enroll in Phase 2 of the study after being diagnosed with gestational diabetes (up to 4 weeks after diagnosis). Their enrollment in the study will start after consent is obtained and continue until 1 week post-delivery. On average we anticipate study participation to be between 8-11 weeks for most participants. Study participants will be approached during a prenatal care visit to the Women's Health Clinic at UConn Health (UCHC), St. Francis Hospital (SFH), and Hartford Healthcare (HH) after being diagnosed with gestational diabetes mellitus (GDM).

### Sample size and justification

We aim to randomize n=40 participants. We may need to consent up to 100 participants to achieve this target N randomized. We may need to randomize up to n=44 participants in the case that a participant drops out soon after randomization.

We plan to randomize 40 participants; using a randomized design, 20 will be assigned to receive the Usual GDM Care plus the Meals 4 Moms intervention (intervention condition) and 20 will be assigned to receive only "Usual GDM Care" (comparison condition).

Based on our previous experiences recruiting the target population, we anticipate that some individuals will consent to participate in the study, but then fail to complete the baseline procedures, decide they no longer want to participate, or deliver early, and thus not be eligible to be randomized.

### Subject Characteristics:

#### **Phase 2:**

Age: between 18-49 years old

Gender: Any gender identity

Ethnicity: Any

Inclusion Criteria:

- 18-49 years old
- Current singleton pregnancy
- GDM diagnosis between 24+0 and 31+6 weeks gestation, and no more than 4weeks from time of diagnosis at time of enrollment.
- Currently receiving gestational diabetes management at the UConn Health Maternal Fetal Clinic, St. Francis Hospital Women’s Health clinic, Hartford Healthcare Women’s Ambulatory Health Services (WAHS)
- Intends to deliver at either UConn Health, St. Francis Hospital or Hartford Healthcare
- Able to read and understand English well enough to participate in the study in English
- Daily access to the internet from smartphone, tablet computer, or laptop/desktop computer that they can use to participate in the study
- Medical clearance to participate from prenatal care provider including clearance to engage in physical activity
- Able to provide verbal or written consent for each component of the study procedures and data collection
- Currently lives within one of the following cities/towns in Connecticut to allow for meal delivery:

Avon	Barkhamsted	Berlin	Bloomfield
Bristol	Burlington	Canton	Cromwell
East Granby	East Hartford	East Windsor	Enfield
Farmington	Glastonbury	Granby	Hartland
Hartford	Manchester	Marlborough	New Britain
Newington	New Hartford	Plainville	Rocky Hill
Simsbury	South Windsor	Southington	Suffield
West Hartford	Wethersfield	Windsor	Windsor Locks

Exclusion Criteria:

- Unable or unwilling to give informed consent or communicate with study staff.
- Diabetes mellitus (Type I or Type II).
- GDM diagnosed prior to 24 weeks gestation or after 32+0 weeks gestation.
- Patient is scheduled for a preterm delivery for medical reasons (i.e., placenta accreta, prior classical incision) at time of eligibility screening or at any time prior to randomization.
- Concurrent participation in another research study providing intervention related to GDM, pregnancy, diet, and/or physical activity.
- Medical conditions that may result in the inability to tolerate solid foods (i.e., hyperemesis gravidarum).
- Medical condition which would prohibit participation as indicated by prenatal care provider providing medical clearance.
- Dietary restrictions that cannot be accommodated for during meal preparation.
- Currently does not live in one of the towns listed within the meal delivery area.
- Has plans to move to out of the meal delivery area between enrollment and expected pregnancy due date.

## **Study Procedures**

### Screening Procedures

Participants will be recruited from the UConn Health, St. Francis Hospital Maternal Fetal Medicine Clinics, and Hartford Healthcare Women's Ambulatory Health Services clinic. Study staff will educate each of the clinics Maternal Fetal Medicine (MFM) clinicians and clinical staff responsible for the care and management of the GDM patients about the study and the opportunity for patients to participate in the study. Clinicians or clinical staff will verbally provide details about participating in the feasibility study to the GDM patients during regularly scheduled clinic visits or phone calls. If the GDM patient indicates they are interested, the clinician or clinical staff member will obtain verbal permission from the GDM patient for a member of the research team to contact them to provide more information about the opportunity to participate or will provide them a recruitment flyer with information on how to contact the study team. Study staff will also post recruitment flyers in the appropriate clinic spaces at each of the recruitment sites (e.g., in the waiting room, examination rooms, and/or bathrooms). The recruitment flyer is enclosed. To track

recruitment and prevent duplicated efforts, a screening log will be maintained to track which GDM patients are approached by MFM clinicians or staff.

Research staff will call interested patients to screen them for eligibility. During this call, staff will obtain verbal permission from the patient to perform a chart review to confirm eligibility (i.e., current patient of UConn Health or St. Francis Hospital Maternal Fetal Medicine Clinic or Hartford Healthcare Women's Ambulatory Health Services clinic, singleton gestation, gestational age at GDM diagnosis, time since GDM diagnosis). Maternal Fetal Medicine Fellows overseeing patient's care at St. Francis Hospital clinic or Hartford Healthcare WAHS clinic will confirm eligibility for study participation. A partial HIPAA Waiver will be submitted for approval to the IRB for phone screening/chart review to determine eligibility. If participants are interested and eligible to participate, research staff will explain the study in more detail, including benefits and potential risks of participation.

Each participant screened for inclusion will be assigned a study identification number sequentially. The link between the study identification number and the patient's contact information will be stored in a password protected file only accessible to relevant study staff. The study identification will not be derived from or include any direct personal identifiers (e.g., name, birthdate, medical record number). The screening log will be password protected and housed on the Obstetrics & Gynecology network drive.

For eligible individuals who decline participation, study staff will keep a list of reasons why.

### **Consent Process**

We request a partial waiver of consent to confirm eligibility screening (via medical chart review or with the referring St. Francis or Hartford Healthcare clinician or clinical staff) for participation in the feasibility study.

Once eligibility has been confirmed and a patient has been confirmed eligible to participate, study staff will conduct an informed consent discussion via phone or virtually using either WebEx or Zoom. A member of the study team will review the consent form with the participant, discuss the research process including why we randomize participants and why follow-up is important, discuss challenges and facilitators of participating in the Meals 4 Moms intervention, and answer any questions the patient has. Following this conversation, staff will email the eligible individual a link to the baseline survey in REDCap. Before proceeding to the survey, participants will review the consent form and provide consent electronically.

As part of the baseline survey, the participant will provide consent for a study team member to contact and obtain medical clearance from a member of the participant's prenatal care team. If medical clearance cannot be obtained within 2 weeks of eligibility screening, the study participant will be considered no longer eligible.

### **Data Collection & Randomization**

Data assessments at baseline will include an online survey (via REDCap), completion of dietary recalls, and obtaining medical clearance.

The baseline survey will include the following measures. A copy of the baseline survey is enclosed. Study staff will review baseline surveys within 48 hours of completion, including scoring the EPDS. See below for procedures for participants who endorse the self-harm item or report elevated depressive symptoms.

- Edinburgh postpartum depression screen (EPDS)
- Newest Vital Sign (nutrition health literacy)
- US HFSSM screening for household food insecurity
- FIGO nutritional questionnaire
- National Health and Nutrition Examination Survey (NHANES) Physical Activity (PAQ) – 2 questions specific to leisure and sedentary behaviors
- Previous use of meal delivery services and digital tools for diet or weight loss
- Demographic, reproductive history, and clinical characteristics

At baseline, participants will also complete 3, 24-hour dietary recalls using the National Cancer Institute's (NCI) automated self-administered 24-hour dietary recall (ASA24™). Participants will complete 3 recalls (2 weekdays, 1 weekend day) within 3 weeks of consent. Study staff will provide via email instructions to each participant will be receive a link to the ASA-24 ([asa24.nci.nih.gov](http://asa24.nci.nih.gov)) along with a username and password that has been generated by the research staff. ASA-24 usernames and passwords will not contain individual identifiers. The usernames will be of alpha-numeric origin (for example, M4M001, M4M002) and not the participant's main study identifier. The passwords will be generated by the ASA-24 system. The study will keep a list of each participant's ASA24 username so we can link ASA24 data to participants' other study data. Participants will be instructed to remember their generated password. In the event a participant is unable to recall their password, they will be advised to reset their password using the ASA-24 system.

Medical clearance. Study staff will obtain medical clearance from the study participant's prenatal care specialist. If staff receive denial of clearance from the prenatal care specialist, they will halt baseline assessments with the potential participant, as denial of medical clearance is an exclusion criterion.

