### **Randomization:**

We will randomize 40 participants 1:1 to the Meals 4 Moms (M4M) and Usual Care (UC) conditions in randomly permuted blocks of size 4 and 6. Randomization will be stratified by site (UCHC vs SFH vs HH) and whether there are children currently living in the participant's home (0 children vs 1+ children) to balance any differences in clinical care and experiences changing diet due to family configuration, respectively. Randomization will be conducted via the randomization module in REDCap based on randomization tables created by [name]. A participant will only be randomized once they have completed all baseline assessments. Study participants will be informed which treatment condition they have been assigned to by a member of the research team.

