#### Psychological Risks:

Participants will be reminded that they do not have to answer any questions they do not wish to in any of the baseline or follow-up assessments. All participant surveys will be completed via a secure web form via REDCap. Participants will be asked to answer some questions about their mood (i.e., depressive symptoms). If the study team finds that answers on the survey are concerning, we will ask the participant to consult with their primary care provider or obstetrician/gynecologist to discuss their symptoms. We also will encourage participants to talk to their prenatal care provider if they feel depressed or experience any unexpected mood changes at any point during the study. If study personnel finds that a participant reports they are a safety concern to themselves or someone else, study staff will need to release the participant's confidential information for emergency care purposes.

Additional efforts to protect participant confidentiality are described below.

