
While not expected to be related to study participation, over the course of the study the research staff may become aware of depressive symptoms among our participants. The study assessment, the Edinburgh Postnatal Depression Scale (EPDS), is screen for depressive symptoms.

- Women who score 12 or greater (suggestive of high risk of clinical depression) and score negative on the EPDS self-harm question (#10) will be contacted by a member of study team. The study team member will encourage the participant to contact their provider to discuss their symptoms and ask for verbal permission to contact the participant's prenatal care provider on their behalf. If study team member will inform

the prenatal care provide that the participant's EPDS score was suggestive for depression.

- Women who score positive on the EPDS suicide question (#10) will be considered at acute risk of injury or harm. In the unlikely event, the study PI or project manager will be contacted immediately, and the participant will be assessed for the need for immediate referral for psychiatric evaluation. Urgent evaluation will be arranged for the participant as indicated, and the participant's provider will be made aware of the situation. Staff will confirm participant's contact information prior to each study follow-up assessment including contact information for their prenatal care provider.

Participants will be made aware of this protocol in the original consent for the study. All referrals will be documented and reported to the study PI.

**Protections Against Risks to Human Subjects:** All adverse events (AE) that are serious, unexpected, and considered related to the study judged by the PI will require expedited reporting. All available information relevant to the evaluation of the serious adverse event (SAE) will be reported.

A SAE is any untoward medical occurrence or effect that at any dose:

- Results in death
- Is life-threatening
- Requires inpatient hospitalization or prolongation of existing hospitalization
- Results in persistent or significant disability/incapacity
- Is a congenital anomaly/birth defect

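### The protocol allows up to 48 hours before staff read a remotely completed baseline survey and describes no faster route for the EPDS self-harm item, which it classes as acute risk

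*Protocol*

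**What the plan says.** **How the survey is taken.** Under Consent Process, "staff will email the eligible individual a link to the baseline survey in REDCap". Under Psychological Risks, "All participant surveys will be completed via a secure web form via REDCap". No staff member need be present when the participant answers.

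**When it is read.** Data Collection & Randomization sets the only stated time limit: "Study staff will review baseline surveys within 48 hours of completion, including scoring the EPDS". The next sentence sends two groups to a later section: "See below for procedures for participants who endorse the self-harm item or report elevated depressive symptoms". It gives neither group its own timing.

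**What happens once it is read.** The EPDS procedure appears in the Risks section, in the text that follows Confidentiality Risks, and has two tiers.
- Score of 12 or more with item 10 negative: the study team contacts the participant, encourages her to speak to her provider, and asks permission to inform the provider on her behalf.
- Item 10 positive: the participant "will be considered at acute risk of injury or harm", "the study PI or project manager will be contacted immediately", and she is assessed for immediate psychiatric referral, with urgent evaluation arranged where indicated.

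**The concern.** The protocol separates the two tiers for response but not for detection. A total score suggesting depression and a positive self-harm answer wait under the same 48-hour limit, although the second is the one the protocol treats as urgent. Staff who follow the text exactly could leave that answer unread for two days.

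What is at stake is participant safety, not the analysis. Item 10 is a single answer that needs no scoring, so the time needed to score the whole scale is no reason to delay noticing it.

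**Working it through.** The 48-hour limit is a procedural commitment, so there is no statistical figure to reproduce. The check is a side-by-side reading of the rules, plus a count of the surveys they cover.

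**1. The sequence for a positive item 10**

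| Step | Timing stated | Where |
|---|---|---|
| Participant submits the web survey | Clock starts | Consent Process; Psychological Risks |
| Staff review the survey and score the EPDS | Up to 48 hours after completion | Data Collection & Randomization |
| PI or project manager contacted | Immediately, once the answer is known | EPDS procedure in the Risks section |
| Assessment for urgent referral | Follows that contact | EPDS procedure in the Risks section |

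Permitted wait from completion to first reading: minimum 0, maximum 48 hours. The immediate step adds nothing to that wait and does not shorten it.

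**2. Search for a faster route**

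The sections on consent, baseline and follow-up data collection, risks and adverse-event reporting contain no automatic alert, no shorter review time for item 10, and no crisis information displayed when it is endorsed. Psychological Risks adds only an untimed step for concerning answers.

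**3. Surveys covered**

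- Inputs: 40 planned and up to 44 randomized, and up to 100 consented (Sample size and justification); 4-5 recruited per month (Feasibility Outcomes table, Protocol and SAP).
- "A participant will only be randomized once they have completed all baseline assessments", so the planned number of completed baseline surveys is at least 40 to 44.
- The upper bound is 100. It should not be fully reached, because some who consent are expected to "fail to complete the baseline procedures".
- If recruited means consented: 4-5 surveys per month.
- If recruited means randomized: 40/5 = 8 months to 40/4 = 10 months. With 100 consents, that is at most 100/10 = 10 to 100/8 = 12.5 surveys per month.

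These counts bound the workload of a faster rule; they do not measure risk. Only surveys with item 10 endorsed would trigger an alert. The documents give no rate for that beyond calling it unlikely, so none is assumed.

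**4. Unfinished surveys**

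The 48-hour clock runs from completion. If a participant answered item 10 and then left the survey unfinished, no review time would apply as written. This is an inference, because item order and REDCap settings are not shown.

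**The case against.** **The two rules might seem to contradict each other.** A reader might set 48 hours against immediate contact and infer an internal conflict. The documents do not support that. The immediate contact is with the PI or project manager and runs from discovery. The gap lies before discovery.

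**The absence may be only apparent.** A reader might also infer that the trial has no alert at all. That cannot be concluded either. The baseline survey is described as enclosed but was not supplied, the REDCap build is not shown, and consent pages were removed before review. An alert or on-screen message may exist in any of these. This objection stands in full: the point is limited to what the protocol text describes, and confidence in it is medium.

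**Other safeguards exist.** Participants are under prenatal care, are told of the EPDS procedure at consent, are encouraged to report mood changes to their provider, and can have information released for emergency care. These are real, and they lower the severity. But each relies on the participant speaking up, on the next visit, or on staff having already read the answer.

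**No standard in the documents makes 48 hours too long, and events should be rare.** Both are true. For the total score, 48 hours is left as it is. For item 10, the argument rests on the protocol's own classification: if the answer calls for urgent action, the plan should provide for seeing it promptly. Rarity also keeps the burden of alerts small.

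**Conclusion.** The point holds as a gap in the written plan. An answer that the protocol itself treats as acute risk may go unread for up to 48 hours after survey completion, and no supplied text describes a quicker route to discovery. It applies to 40 to 44 planned baseline surveys, with 100 as a ceiling.

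The conclusion rests on two assumptions: that the supplied text is the whole of the written procedure for reading the survey, and that staff may use the full window it allows. It does not rest on any assumed item 10 rate, and no number of events or amount of harm from delay is claimed. The change is worth making because a stated rule gives a weaker safeguard than a cheap alternative would. The existing safeguards and the possibility of an undocumented alert keep it from being more serious than that.

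**What to change.** In Data Collection & Randomization:

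1. Keep the 48-hour review as the outer limit for all baseline surveys and for scoring the total EPDS.
2. For item 10, add an automatic REDCap alert to the PI or project manager on any positive answer, with crisis resources shown on screen at that point. Preferably the alert fires when the answer is saved, so that an unfinished survey is also covered.
3. State that the existing EPDS procedure then starts the same day or, if the alert arrives out of hours, at the next staffed opportunity, and never later than 48 hours.

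The alert should be added to the 48-hour limit and not replace it. A rule requiring action only once an alert has been seen would have no outer bound.

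Apply the same rule to the follow-up survey if it contains the EPDS. The Post-intervention survey section says that many baseline measures are repeated, but it does not confirm the EPDS and gives no review time. If the REDCap build or enclosed survey already has such an alert, one sentence in the protocol stating it is enough.

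**Cost.** An alert setting, a line of on-screen text and a short wording amendment. The PI and project manager are already named as responders, so no new staff are needed. The downside is occasional alerts for existing staff, some out of hours. The sample size, randomization and analysis do not change.
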